		Week 1 (Day 1)	Week 3 (Day 15)	Week 5 (Day 29)	Week 7 (Day 43)	Week 9 (Day 57)	Week 11 (Day 71)	Week 13 (Day 85)	> Week 13 (Day 85)	Within 7 Days of Decision to Discontinue	Visit 30 Days (± 5 days) After Last Tx	Phone Call 90 Days (± 5 days) After Last Tx	Every 12 Weeks (± 1 Week) After Last Tx
Concomitant medications and procedures f	X	Concomitant medications and procedures are collected through the Safety Follow-up Visit									X		
AE collection k		AEs are collected through the Safety Follow-up Visit Treatment-related non-serious AEs are collected until the 90-day Safety Follow-up Phone Call. b										X	
SAE collection k		All SAEs are documented through the 90-day Safety Follow-up Phone Call Ongoing SAEs at the 90-day Safety Follow-up Phone Call will be followed up b										X	
Samples and Laboratory Assessmentsl													
Hematology m	X	X	X	X	X	X	X	X	Q2 weeks	X	X		
Lymphocyte subset quantification n		X		X						X			
Coagulation (hemostaeology) o	X	X	X	X		X		X	Q4 weeks (odd- numbered cycles only)	X	X		
Full serum chemistry p	X	X								X	X		
Core serum chemistry p			X	X	X	X	X	X	Q2 weeks				
Urinalysis q	X	X		X		X		X	Q4 weeks	X	X		
Pregnancy test r	X	X		X		X		X	Q4 weeks	X	X		
T4 and TSH s	X	X		X				X	Q8 weeks	X			
Blood for cytokines t		X	X	X		X				X			
Blood for vaccination-related antibodies u		X						X		X			
HBV and HCV screening tests v	X												

		Treatment Period* (-3/+1 days) 1 Cycle = 14 Days								End Of Treatment/Follow-Up b			
Assessments	Screening (≤ 28 Days Prior to Enrollment)	Cycle 1	Cycle 2	Cycle 3	Cycle 4	Cycle 5	Cycle 6	Cycle 7	Until EOT	EOT/ Withdrawal Visit b	Safety Follow-up c		Survival Follow-up d
		Week 1 (Day 1)	Week 3 (Day 15)	Week 5 (Day 29)	Week 7 (Day 43)	Week 9 (Day 57)	Week 11 (Day 71)	Week 13 (Day 85)	> Week 13 (Day 85)	Within 7 Days of Decision to Discontinue	Visit 30 Days (± 5 days) After Last Tx	Phone Call 90 Days (± 5 days) After Last Tx	Every 12 Weeks (± 1 Week) After Last Tx
CCI CCI													
Baseline tumor evaluation/staging (CT/MRI/other established methods) x	X												

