- End of treatment/follow-up: All subjects will have an EOT Visit within 7 days after the decision to discontinue study treatment. All AEs will be documented during the 30-day Safety Follow-Up Visit and the 90-day Safety Follow-up Phone Call. All SAEs and all treatment-related nonserious AEs need to be documented through the study's Safety Follow-up Phone Call, defined at 90 days (± 5 days) after the last IMP administration. Subjects with an ongoing SAE at the 90-day Safety Follow-up Phone Call must be monitored and followed by the Investigator until stabilization or until the outcome is known, unless the subject is documented as "lost to follow-up." Any SAE assessed as related to avelumab must be reported whenever it occurs, irrespective of the time elapsed since the last administration of avelumab. Subjects without PD at the EOT Visit will be followed up for disease progression (CT/MRI scans every 8 weeks for the first 24 weeks of treatment, then every 12 weeks) or the start of subsequent anticancer therapy (whichever comes first). In addition, subjects will be followed every 12 weeks (± 1 week) for survival (including assessment of any further tumor therapy); see footnote d.
- Safety Follow-up: During the post-treatment Safety Follow-up Visit, serious and non-serious AEs that the Investigator believes to have at least a reasonable possibility of being related to study drug will be recorded in the eCRF. If another antineoplastic therapy is administered before the end of the 30-day period, the 30-day Safety Follow-up visit should be conducted, if possible, prior to the start of this new therapy.
- Survival follow-up: After discontinuation of study treatment, post-study survival status will be collected every 12 weeks ± 1 week until the subject's death, until 12 months after termination of treatment of the last subject, or until end of study, whichever occurs first. Follow-up will include collection of information on subsequent anticancer therapies. Telephone contact is acceptable.
- Physical examination: A full physical examination should be performed at Screening and at the EOT Visit. Physical examinations at all other visits should be directed to signs and symptoms. If the physical examination at Screening is performed within 3 days of C1D1, it does not have to be repeated at C1D1. Weight is measured at every visit, and height is measured at Screening and every 4 weeks thereafter.

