  - k. Adverse event assessments: AEs should be documented and recorded at each visit using the NCI-CTCAE version 4.03. For SAEs, the active reporting period will begin from the time that informed consent/assent is provided, which is obtained prior to the subject's participation in the study (ie, prior to undergoing any study-related procedure and/or receiving study treatment) through and including 90 calendar days ( $\pm$  5 days) after the last dose of study treatment. SAEs occurring to a subject after the active reporting period has ended should be reported to the Sponsor if the Investigator becomes aware of them; at a minimum, all SAEs that the Investigator believes have at least a reasonable possibility of being related to avelumab are to be reported to the Sponsor. Serious and non-serious AEs should be recorded on the eCRF from the time the subject has taken at least 1 dose of study treatment through the subject's last visit. If a subject begins a new anticancer therapy, the AE reporting period for non-serious AEs ends at the time the new treatment is started. Death must be reported if it occurs during the SAE reporting period after the last dose of study treatment, irrespective of any intervening treatment. During the post-treatment Safety Follow-up (beyond 30 days through 90 calendar days after last dose of study treatment), serious or non-serious AEs suspected to be related to avelumab based on the Investigator's assessment should be recorded on the eCRF.
  - l. Laboratory assessments: On those weeks when no other assessments are required as per the Schedule of Assessments, a visit to the clinical site is not required unless the Investigator considers it necessary.
  - m. Hematology: Complete blood count results must be available and reviewed prior to dose administration. No need to repeat on CID1 if Screening assessments were performed within 7 days prior to that date.
  - n. Lymphocyte subset quantification: T-cell population; T-cell, B-cell, and NK-cell numbers.
  - o. Coagulation (hemostaseology): No need to repeat on CID1 if Screening assessments were performed within 7 days prior to that date.

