#### 7.1.4 Safety Follow-up

Follow-up with each subject will be conducted 30 days ( $\pm 5$  days) and 90 days ( $\pm 5$  days) after the last dose of avelumab. The 30-Day Safety Follow-up Visit should be performed at the trial site; the 90-Day Safety Follow-Up can be performed via telephone contact. Each follow-up will include an assessment of safety parameters as described in Table 1. All SAEs and all treatment-related nonserious AEs need to be documented through the study's 90-day Safety Follow-up Phone Call.

During the post-treatment safety follow-up period, AEs and SAEs that the Investigator believes have at least a reasonable possibility of being related to study drug are to be recorded on the eCRF.

Any SAE assessed as related to study treatment must be reported whenever it occurs, irrespective of the time elapsed since the last administration of study treatment. Subjects or their legal representative will also be asked about any antitumor therapy.

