## **8.5.2 Analyses of Primary Endpoints**

### **8.5.2.1 Phase I: Occurrence and Severity of Treatment-emergent Adverse Events $\geq$ Grade 3**

Adverse events will be coded according to Medical Dictionary for Regulatory Activities (MedDRA). Severity of AEs will be graded using the NCI-CTCAE v4.03 toxicity grading scale.

Adverse events (serious and nonserious) will be considered TEAEs when emerging or worsening in the on-treatment period, defined as the time from the first trial drug administration to the last drug administration date + 30 days or the earliest date of subsequent anticancer drug therapy minus 1 day, whichever occurs first, unless otherwise stated.

The frequency of subjects experiencing TEAEs  $\geq$  Grade 3, regardless of relatedness to trial treatment, will be summarized by system organ class and preferred term at each dose level and described in terms of severity. Similar summaries will also be provided for TEAEs  $\geq$  Grade 3 related to trial treatment.

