Subjects who start treatment and discontinue from the study on the same day may have two different sets of data collected on study day 1 (one during study and one in the End of Treatment (EOT) visit). Data reported at the EOT visit are not eligible for baseline selection.

If a scheduled pre-dose measurement actually occurred post-dose, then the corresponding measurement will be treated and analyzed similar to an unscheduled post-dose measurement.

Baseline for HR and QT/QTc assessments will be derived from the visit where both HR and QT are not missing. QTcF will be derived based on HR and QT.

Definition of study day:

Study day is defined relative to the date of start of treatment. Study day 1 defines the day of first administration with avelumab, the day before is defined as study day -1 (no study day 0 is defined).

Definition of on-treatment period:

The on-treatment period is defined as the time from the first dose of study treatment through minimum (30 days + last dose of study treatment, start day of new anti-cancer drug therapy - 1 day).

The date of new anti-cancer drug therapy after start date is derived as outlined in Section 12.1.

Definition of duration:

Duration will be calculated by the difference of start and stop date + 1 (e.g. survival time (days) = date of death - date of first dose of study drug + 1).

The time since an event (e.g. time since first diagnosis) will be calculated as reference date minus date of event.

Standard derivations and reporting conventions:

The following conversion factors will be used to convert days into months or years:

1 week = 7 days, 1 month = 30.4375 days, 1 year = 365.25 days.

Demographic and physical measurements:

- Age [years]:
 - (date of given informed consent - date of birth + 1) / 365.25
 - In case only year and month of birth are given: Age [years]: (year/month of given informed consent - year/month of birth) / 12
 - In case only year of birth is given: Age [years]: (year of given informed consent - year of birth)

The integer part of the calculated age will be used for reporting purposes.

- BMI (kg/m^2) = weight (kg)/[height (m)]².
- BSA (m^2) = ([height (cm) × weight (kg)] / 3600)^{0.5} (1)

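### AE-recording instructions conflict inside the primary-endpoint window: Table 1 footnote c and Section 7.1.4 name only possibly related events, while other passages ask for all AEs

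*Protocol*

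**What the plan says.** **The endpoint.** Protocol Section 8.5.2.1 makes Grade ≥ 3 TEAEs a Phase I primary endpoint. Their frequency, "regardless of relatedness to trial treatment, will be summarized by system organ class and preferred term at each dose level", has this window: "from the first trial drug administration to the last drug administration date + 30 days". The window closes sooner if another anticancer drug is started, on the day before that start. SAP Section 9 agrees: "The on-treatment period is defined as the time from the first dose of study treatment through minimum (30 days + last dose of study treatment", with the same early end.

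**Passages that name possibly related events for recording.**
- Table 1 footnote c, which is keyed to the columns for contacts after treatment, reads: "During the post-treatment Safety Follow-up Visit, serious and non-serious AEs that the Investigator believes to have at least a reasonable possibility of being related". Events so judged are to go into the eCRF.
- Section 7.1.4, second paragraph, has similar wording: "AEs and SAEs that the Investigator believes have at least a reasonable possibility of being related to study drug are to be recorded". It covers all contacts after treatment ends.

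**Passages with no causality condition up to 30 days.**
- Table 1, AE collection row: "AEs are collected through the Safety Follow-up Visit". After that visit the row keeps related non-serious AEs until the 90-day call.
- Table 1 footnote b, directly above footnote c: AEs of any cause, at both the 30-day visit and the 90-day call.
- Table 1 footnote k: serious and non-serious AEs from the first dose to the last visit. The wording on related events comes later, under "During the post-treatment Safety Follow-up (beyond 30 days through 90 calendar days after last dose of study treatment").
- Section 7.4.1.3: the AE reporting period runs from consent to the 90-day call.
- Section 7.1.3.1: AEs are documented at the End of Treatment (EOT) Visit.

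**The concern.** The endpoint is defined so that attribution plays no part. If some sites apply a causality filter when entering events at the 30-day visit and others do not, attribution re-enters through data collection, by an amount that depends on which passage each site followed. About 50 sites are planned for 12 to 36 Phase I subjects, so differences in practice would not average out.

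The analysis cannot repair this. SAP Section 9 evaluates data as observed, without imputation unless otherwise specified, and an event never entered leaves no trace. SAP Section 15.2.1 tabulates Grade ≥ 3 TEAEs both overall and for related events. Filtering would lower the first count and leave the second alone, so the related share would look larger than it is.

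**Working it through.** The plan gives no figure to reproduce. The check is a comparison of texts, followed by arithmetic on how much time and weight are involved.

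**1. Which visit footnote c means.** Table 1 splits Safety Follow-up into a visit at 30 days (± 5) and a telephone call at 90 days (± 5). Footnote c speaks of the visit, and its next sentence deals with the 30-day period. It therefore concerns the 30-day visit, the last planned face-to-face contact for events inside the endpoint window.

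**2. Whether the passages can be reconciled.** Footnote k starts the related-event wording after Day 30, outside the window. Footnote c attaches it to the visit at which events up to Day 30 are collected. Footnote b asks for AEs of any cause at that same visit. If every AE is recorded there, naming a related subset does nothing, so a coordinator may reasonably take footnote c as a limit. No passage says which one prevails.

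**3. Which events are exposed.**
- SAEs of any cause are documented to the 90-day call (Section 7.1.4, first paragraph).
- Clinical Grade 4-5 AEs are SAEs by Sponsor convention (Section 7.4.1.1), so they are safe.
- Events reported at the EOT Visit are documented without a causality condition.
- What remains is unrelated, non-serious Grade 3 AEs, and non-serious Grade 4 laboratory AEs, mainly those arising after the EOT Visit and by Day 30.

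**4. How long that interval is.** For n doses on schedule the endpoint window is 14(n − 1) + 1 + 30 days. The EOT Visit falls within 7 days of the decision to stop, so its distance from the last dose is not fixed. I assume 0 days (an upper bound), 14 days (decision and visit when the next dose is due) or 21 days (14 + 7).

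| Doses | Window (days) | EOT at +0 | EOT at +14 | EOT at +21 |
|---|---|---|---|---|
| 2 | 45 | 30/45 = 67% | 16/45 = 36% | 9/45 = 20% |
| 4 | 73 | 30/73 = 41% | 16/73 = 22% | 9/73 = 12% |
| 8 | 129 | 30/129 = 23% | 16/129 = 12% | 9/129 = 7% |

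These are shares of calendar time, not of events. New anticancer drug therapy started before Day 30 shortens the interval further.

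**5. The weight of one subject.** 1/36 = 2.8 and 1/12 = 8.3 percentage points. A missed event moves the overall rate only if that child has no other Grade ≥ 3 TEAE.

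**6. A visit held early.** With the ± 5-day window the 30-day visit may fall on Day 25. Under the AE row alone, unrelated non-serious events on Days 26 to 30 (5 days) would not be collected. Footnote b and Section 7.4.1.3 extend collection to the 90-day call and cover those days. The gap exists only where the row is followed by itself.

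**The case against.** The best reply is that the plan, read as a whole, already asks for these events. The word only appears in neither footnote c nor Section 7.1.4. Footnote b, immediately above footnote c, covers AEs of any cause at the 30-day visit, and footnote k and Section 7.4.1.3 agree with it. A reader might infer that the protocol leaves unrelated late events uncollected. The documents do not support that: several passages require them, and footnote c is the outlier.

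Footnote k also describes post-treatment safety follow-up as the time beyond 30 days. On that definition the sentence in Section 7.1.4 falls outside the endpoint window. This helps Section 7.1.4, although that section's own opening sentence includes the 30-day contact in follow-up. It does not help footnote c, which refers to the 30-day visit itself.

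The practical reach is limited too. The exposed class is narrow, progression symptoms and many laboratory findings are generally not AEs (Section 7.4.1.1), the endpoint is descriptive, and the dose decision rests on avelumab-attributable DLTs in the first 28 days, which this wording does not touch. Section 7.4.1.2 sends sites to eCRF conventions that are not among these documents and may settle the matter in practice.

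All of this limits the size of the problem. It does not remove the contradiction, because a site can follow footnote c as written and filter a primary endpoint by attribution.

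**Conclusion.** The point holds as an inconsistency in recording instructions, with a risk of uneven under-recording of unrelated, non-serious Grade 3 AEs (and non-serious Grade 4 laboratory AEs), mainly between the EOT Visit and Day 30. The direction is known: the all-cause frequency can only fall. The size is not, because the documents give no rate for these events and do not show which passage sites follow.

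Two further inferences should be resisted. The time shares above are not estimates of missed events; they show only that the interval is not negligible for children who stop early, and they rest on on-schedule dosing and an assumed EOT timing. Nor is there a gap after a Day 25 visit on the fullest reading of the plan, since footnote b already reaches the 90-day call.

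**What to change.** Reword Table 1 footnote c and the second paragraph of Section 7.1.4 to match footnote k: record all AEs, related or not, through 30 days after the last dose, or until new anticancer drug therapy starts if that is earlier. The related-only rule for non-serious AEs then applies only after Day 30.

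Align the AE collection row with footnote b, so that when the 30-day visit is held before Day 30, AEs up to Day 30 are captured at the 90-day call that is already planned.

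The cost is wording changes and slightly more AE entry, with no added visit. The change works only going forward; it cannot restore events that were never entered.

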### 6.5.3 Other Interventions

The following nondrug therapies must not be administered during the trial and within 28 days before the start of trial treatment: major surgery (excluding prior diagnostic biopsy).

Prior palliative radiotherapy to metastatic lesions is permitted, provided it has been completed 48 hours prior to subject registration.

Palliative short-course, limited-field, bone-directed radiotherapy may be administered during the trial. The assessment of PD will be made according to RECIST 1.1 (Eisenhauer 2009) and as adjudicated by the Investigator and not based on the necessity for palliative bone-directed radiotherapy.

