#### 7.4.1.3 **Definition of the Adverse Event Reporting Period**

The AE reporting period for safety surveillance will begin when the subject is initially included in the trial (date of first signature of informed consent) and continue through the 90-Day Safety Follow-up Phone Call, which is defined as occurring 90 days ( $\pm$  5 days) after last study drug administration.

Any SAE assessed as related to IMP must be reported whenever it occurs, irrespective of the time elapsed since the last administration of IMP.

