15.2.1 All Adverse Events

Adverse events will be summarized by worst severity (according to NCI-CTCAE version 4.03) per subject, using the latest version of MedDRA PT as event category and MedDRA primary SOC body term as Body System category.

In case a subject has events with missing and non-missing grades, the maximum of the non-missing grades will be displayed. No imputation of missing grades will be performed.

The following tables will be created:

- The overall summary of AEs table will include the frequency (number and percentage) of subjects with each of the following by dose level:
 - TEAEs
 - Related TEAEs
 - Serious TEAEs
 - Related Serious TEAEs
 - TEAEs, Grade ≥ 3 (primary endpoint)
 - Related TEAEs, Grade ≥ 3
 - TEAEs leading to permanent treatment discontinuation
 - Related TEAEs leading to permanent treatment discontinuation
 - TEAEs leading to death
 - Related TEAEs leading to death
 - Treatment-emergent irAEs
 - Treatment-emergent IRRs
 - Related treatment-emergent IRRs
- TEAEs by SOC and PT and worst grade (secondary endpoint)
- Related TEAEs by SOC and PT and worst grade (secondary endpoint)
- TEAEs leading to death by SOC and PT
- Related TEAEs leading to death by SOC and PT

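### Conflicting stop rules for non-serious AEs may leave part of the primary Grade 3 or higher TEAE window unrecorded after radiotherapy or surgery

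*Protocol*

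**What the plan says.** **Recording.** Footnote k of protocol Table 1 states: "If a subject begins a new anticancer therapy, the AE reporting period for non-serious AEs ends at the time the new treatment is started". It does not restrict this to drugs. Footnote c and Section 7.1.4 say that AEs recorded in post-treatment follow-up are those the investigator thinks may be related to study drug. Section 7.1.4 also says: "All SAEs and all treatment-related nonserious AEs need to be documented through" the 90-day call. Footnote b asks for all AEs at both the 30-day visit and the 90-day call. The Table 1 AE row and Section 7.4.1.3 give recording periods with no stop at new therapy.

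**Analysis.** Protocol 8.5.2.1 defines the primary Grade 3 or higher TEAE window as running from the first dose to "last drug administration date + 30 days or the earliest date of subsequent anticancer drug therapy minus 1 day, whichever occurs first", and counts events whatever their relationship to treatment. SAP Section 9 uses the same limit: "start day of new anti-cancer drug therapy - 1 day". SAP 12.1 shows that the word drug is deliberate: the first new anticancer drug closes the on-treatment period, while the first new anticancer therapy of any kind is used only for efficacy censoring. The general definition in protocol 8.5.1 closes the period at any new anticancer therapy, but only where nothing else is stated; 8.5.2.1 states something else.

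**The concern.** The event that ends recording is broader than the event that ends the analysis window. Radiotherapy is named as anticancer treatment in Exclusion Criterion 2 (protocol 5.3.2), and SAP 12.1 takes post-discontinuation radiotherapy and surgery from their own eCRF pages. Either could end non-serious AE recording at a site that applies footnote k, while the subject stays inside the primary window. An event that is not recorded is analysed as no event, and the SAP has no step that would detect this.

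A primary safety endpoint is at stake, in a Phase I part of 12 to 36 children. Sites that follow different sentences of the same protocol would also collect different data.

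**Working it through.** The plan states no figure to reproduce. The check sets the rules side by side and counts days.

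| Source | Governs | Closed by new therapy? | Other limits |
|---|---|---|---|
| Protocol Table 1, footnote k | Recording | Yes, any anticancer therapy (non-serious AEs) | Suspected-related AEs only, from day 30 to day 90 |
| Table 1, footnote b | Recording | No | All AEs at the 30-day visit and 90-day call |
| Table 1, AE row | Recording | No | All AEs to the Safety Follow-up Visit; related non-serious AEs to the 90-day call |
| Footnote c; 7.1.4 | Post-treatment recording | No | Suspected-related AEs; 7.1.4 adds all SAEs |
| 7.4.1.3 | Reporting period | No | Consent to the 90-day call |
| 7.4.1.6 | AE follow-up | No | Any AE, outcome assessed at the 90-day call |
| 8.5.1 | General on-treatment period | Yes, any therapy, unless stated otherwise | Last dose + 30 days |
| 8.5.2.1 | Primary TEAE window | Drug therapy only | Last dose + 30 days, related or not |
| SAP 9 and 12.1 | On-treatment period | Drug therapy only | Last dose + 30 days |

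**Length of the gap.** Let radiotherapy or surgery fall on day d after the last dose, with d from 1 to 30 and no new anticancer drug by day 30. The primary window stays open to day 30. Under footnote k the days without non-serious recording are d to 30, that is 30 − d + 1 = 31 − d.

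- d = 1: 31 − 1 = 30 days
- d = 15: 31 − 15 = 16 days
- d = 30: 31 − 30 = 1 day
- If the site follows 7.4.1.3 instead, recording continues and the gap is 0 days.
- If 8.5.1 governed the analysis, the window would close on day d − 1 and the gap would also be 0. It does not govern the primary endpoint, because 8.5.2.1 overrides it.

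**Which events.** Under the sponsor's convention in protocol 7.4.1.1, clinical Grade 4 and 5 events are reported as SAEs, so they stay collected. A Grade 4 laboratory abnormality is serious only if it meets a seriousness criterion. The exposure is therefore non-serious Grade 3 AEs and non-serious Grade 4 laboratory AEs. The laboratory values themselves still reach the graded tables of SAP 15.4.1, whose 30-day window has no cut at new therapy, but they would not count as TEAEs.

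**Footnote c and 7.1.4.** Read on their own, these would drop unrelated non-serious AEs after the last dose in any subject, with or without new therapy. Footnote k describes post-treatment safety follow-up as days 30 to 90, which would confine the restriction to days outside the primary window. Footnote c, however, applies it at the safety follow-up visit, which Table 1 places at day 30. The protocol does not settle this.

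**Scale.** The endpoint is the proportion of subjects with at least one such event. One subject whose only Grade 3 or higher TEAE falls in the gap lowers it by 1/36 = 2.8 points with 36 subjects and by 1/12 = 8.3 points with 12. Lost events cannot raise the proportion, so any bias is downward.

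**The case against.** The strongest reply is that most of the protocol does not stop recording. Footnote b, the AE row, 7.4.1.3 and 7.4.1.6 all run past the start of new therapy, and a site that follows them has no gap. This stands: the text does not establish that events go uncollected, only that they may. Footnote k is nevertheless the one sentence that addresses new therapy directly, so a site could reasonably treat it as controlling. Footnote c asks for the 30-day visit before new antineoplastic therapy where possible; that brings the contact forward but does not cover the days after it.

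Several stronger readings are tempting, and the documents do not support them.

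- *Radiotherapy during treatment.* Section 6.5.3 says "Palliative short-course, limited-field, bone-directed radiotherapy may be administered during the trial", so a reader might infer that recording stops while the child is still on avelumab. This is strained. The sentence in footnote k sits among text about the period after the last dose, the same footnote asks for AEs at each visit, the SAP takes subsequent therapy from post-discontinuation pages, and Exclusion Criterion 2 excepts this radiotherapy. It is still worth ruling out in words.
- *A rate over days at risk.* The endpoint is per subject. A child already counted for another Grade 3 or higher TEAE changes nothing in the overall proportion.
- *A percentage of irradiated children with a missed event.* That needs an event rate and a frequency of early radiotherapy or surgery. The documents give neither.
- *Loss of late immune-related events.* Footnote k itself keeps suspected-related AEs from day 30 to day 90, and the summary tables in SAP 15.3.3 are confined to treatment-emergent events.
- *The start of recording.* Footnote k starts at first dose and 7.4.1.3 at consent. Events before the first dose are not TEAEs unless they worsen on treatment, so this does not materially touch the endpoint.

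One could instead cut the analysis at any new therapy, as 8.5.1 does. That would align the windows and limit confounding by radiotherapy or surgical toxicity. It would also reverse a distinction that 8.5.2.1 and SAP 12.1 draw on purpose.

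**Conclusion.** The conflict holds and bears on a primary endpoint. The size of the resulting bias is unknown and may be near zero. A gap arises only when a site follows footnote k, radiotherapy or surgery comes within 30 days of the last dose, and no new anticancer drug has already closed the window. It is then at most 31 − d days. It changes the result only for a subject whose sole Grade 3 or higher TEAE is non-serious and falls in those days. The direction is certain: downward. The 2.8 to 8.3 points are the effect of one such subject in 36 to 12, not an estimate of how many there are. The restriction to suspected-related events in footnote c and 7.1.4 is part of the same conflict, because the primary endpoint counts unrelated events too.

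**What to change.** Reconcile footnotes b, c and k of Table 1 and Sections 7.1.4, 7.4.1.3 and 8.5.1 with Section 8.5.2.1 and SAP Sections 9 and 12.1. The common rule should state that:

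- All non-serious AEs, related or not, are recorded at least until 30 days after the last dose or the day before a new anticancer drug, whichever is first. If 7.4.1.3 and footnote b are meant to carry unrelated events to day 90, say so everywhere.
- Radiotherapy, including that permitted in 6.5.3, and surgery do not end recording.
- Treatment-related non-serious AEs are recorded to the 90-day call whatever therapy follows.
- The on-treatment period in 8.5.1 closes early at new anticancer drug therapy.

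The cost is wording in the protocol and the eCRF completion guideline, and a few more AE entries per subject. The reported Grade 3 or higher proportion may become slightly less favourable.

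The modification history in SAP version 2.0 (June 2021) says that evaluation of monotherapy ended after Phase I, so new wording would recover little data already missed. For the Phase I report, the dates on the post-discontinuation radiotherapy and surgery pages can be used to count the subjects with either within 30 days of the last dose and before any new drug. Reporting that count would show whether the gap matters.
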